Will study data or test results be recorded in the subject's medical records?

Yes

Will results of specific tests and/or results of the overall study be revealed to the research subject and or his/her doctor?
Yes, all positive and negative results will be revealed to the research subject and their doctors. The CLIA reports will be available to upload into EMR system.

Please identify all third parties, including the subject's physician, to receive the test results.
Subject and subject's physicians.

SAMPLE: Buccal Brushing

What is the purpose of the sample collection?
DNA collection for genetic studies.

For blood draws, specify the amount drawn, in teaspoons, at each visit and across the course of the subjects entire participation time.
N/A

Is there the possibility that cell lines will be developed with this sample?No

Sample will be obtained from:
Pathology, Clinical Labs, Research Labs

Will the sample be stripped of identifiers?
No

If sample will be released outside the hospital:

Will sample be released to anyone not listed as an investigator on the protocol? Will the information be identifiable, coded or de-identified?
Yes, coded samples may be transferred after formal Materials Transfer Agreement

Will sample material be sold or transferred to any third parties? Will the information be de-identified?
The transfer would be done only after formal material transfer agreement. Samples will not be sold

If sample will be banked for future use:

Where will the sample be banked and for how long?
Samples will be banked indefinitely at Baylor College of Medicine

Does the banking institution have an approved policy for the distribution of samples?
Yes

If the entire sample will NOT be used during the course of this research study:

Will the remaining tissue be discarded? If not what will be done with the remaining sample after study completion and how long will the sample be kept?
The remaining tissue will not be discarded. The samples would be kept indefinitely

Will samples be made available to the research subject (or his/her medical doctor) for other testing?
No

If a subject withdraws from the study:

Will subject have the option to get the remaining portion of their sample back?
No

Will samples be destroyed? If not, will they be kept anonymously? What will happen to the sample if the subject revokes authorization?
Samples will be kept encoded. If a subject withdraws from the study, their samples will be destroyed.

Will data obtained from their sample be deleted? What will happen to the sample if the subject revokes authorization?
The data collected may not be deleted. The sample will be destroyed if the subject revokes.

Will study data or test results be recorded in the subject's medical records?
Yes

Will results of specific tests and/or results of the overall study be revealed to the research subject and or his/her doctor?
Yes, all positive and negative results will be revealed to the research subject and their doctors. The CLIA reports will be available to upload into EMR system.

Please identify all third parties, including the subject's physician, to receive the test results.

Subject and subject's physicians.

SAMPLE: Skin

What is the purpose of the sample collection?

DNA and RNA collection for genetic studies.

For blood draws, specify the amount drawn, in teaspoons, at each visit and across the course of the subjects entire participation time.

N/A

Is there the possibility that cell lines will be developed with this sample? Yes

Sample will be obtained from:

Pathology, Clinical Labs, Research Labs

Will the sample be stripped of identifiers?

No

If sample will be released outside the hospital:

Will sample be released to anyone not listed as an investigator on the protocol? Will the information be identifiable, coded or de-identified?

Yes, coded samples may be transferred after formal Materials Transfer Agreement

Will sample material be sold or transferred to any third parties? Will the information be de-identified?

The transfer would be done only after formal material transfer agreement. Samples will not be sold

If sample will be banked for future use:

Where will the sample be banked and for how long?

Samples will be banked indefinitely at Baylor College of Medicine

Does the banking institution have an approved policy for the distribution of samples?

Yes

If the entire sample will NOT be used during the course of this research study:

Will the remaining tissue be discarded? If not what will be done with the remaining sample after study completion and how long will the sample be kept?

The remaining tissue will not be discarded. The samples would be kept indefinitely

Will samples be made available to the research subject (or his/her medical doctor) for other testing?

No

If a subject withdraws from the study:

Will subject have the option to get the remaining portion of their sample back?

No

Will samples be destroyed? If not, will they be kept anonymously? What will happen to the sample if the subject revokes authorization?

Samples will be kept encoded. If a subject withdraws from the study, their samples will be destroyed.

Will data obtained from their sample be deleted? What will happen to the sample if the subject revokes authorization?

The data collected may not be deleted. The sample will be destroyed if the subject revokes.

Will study data or test results be recorded in the subject's medical records?

Yes

Will results of specific tests and/or results of the overall study be revealed to the research subject and or his/her doctor?

Yes, all positive and negative results will be revealed to the research subject and their doctors. The CLIA reports will be available to upload into EMR system.

Please identify all third parties, including the subject's physician, to receive the test results.

Subject and subject's physicians.

Section O: Drug Studies

Does the research involve the use of ANY drug* or biologic? (*A drug is defined as any substance (other than food) that is used to elicit a pharmacologic or physiologic response whether it is for treatment or diagnostic purposes)

No

Does the research involve the use of ANY gene transfer agent for human gene transfer research?

No

O1. Current Drugs

Is this study placebo-controlled?

No

Will the research involve a radioactive drug?

No

Section P: Device Studies

Does this research study involve the use of ANY device?

No

Section Q: Consent Form(s)

Genetic study to determine the cause of birth defects in newborns in Texas

Section R: Advertisements

None

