Birth defects, including structural and functional anomalies, are the leading cause of neonatal mortality and a significant cause of pediatric hospitalizations worldwide, affecting about 7.9 million children annually. In developed countries, congenital anomalies account for approximately 13% of NICU admissions. Genetic origins are suspected in 30% of these cases, with half of the sick neonates lacking an identified genetic cause. Advances in molecular technologies, such as whole-genome sequencing (WGS), have transformed the diagnosis and treatment of genetic disorders in neonates. Rapid WGS has provided diagnoses in 36% to 57% of infants, significantly influencing clinical decision-making. However, many NICUs in Texas lack resources for comprehensive genetic evaluation. Without a genetic diagnosis, families remain uninformed about recurrence risks, and medical decisions may be made without genomic insights. To address these gaps, we will use an academic virtual consultation platform, called Consultagene (www.consultagene.org) to reach the under-resourced NICUs at the Texas-Mexico border and other parts of Texas, aiming to provide low-cost genetic testing and improve genomic care for vulnerable neonatal populations in NICUs in Texas. Consultagene was developed at BCM to improve access to genomic care and education for individuals with limited access to a genetics specialist. This virtual platform offers comprehensive services, including patient scheduling, medical document sharing, interpretation of genetic test results, tele-genetic counseling, and educational videos for patients and healthcare providers, which are available in multiple languages including Spanish.

Section D: Purpose and Objectives

The purpose of this protocol is to:

1. Deliver virtual genetic evaluation through Consultagene and low-cost trio whole genome sequencing (WGS) RNAseq, and metabolomic studies for critically-ill newborns in under-resourced NICUs at the Texas-Mexico border, particularly in El Paso and Rio Grande Valley (RGV) and other parts of Texas.
2. Determine the effectiveness of Consultagene in under-resourced NICUs via surveys and clinician interviews.

Section E: Protocol Risks/Subjects

E1. Risk Category

Category 1: Research not involving greater than minimum risk.

E2. Subjects

Gender:

Both

Age:

Adult (18-64 yrs), Infant/Toddler (0-36 mos), Premature Infant (<37 weeks gestational age)

Ethnicity:

All Ethnicities

Primary Language:

English, Spanish

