Groups to be recruited will include:

Both patients and healthy, non-patient, normals

Which if any of the following vulnerable populations will be recruited as subjects?

Children, Employees or lab personnel

Vulnerable populations require special protections. How will you obtain informed consent, protect subject confidentiality, and prevent undue coercion?

Parents will provide informed consent for participation of their children in the study. This would prevent undue coercion of this vulnerable population. Subject confidentiality would be maintained by coding of all specimens. Family participation would be entirely voluntary.

To protect employees' participating in interviews, the study team will ensure confidentiality by anonymizing responses and storing data securely. Participation will be voluntary, with verbal consent obtained (see section S). Interviews will take place in a private setting.

E3. Pregnant woman/fetus

Will pregnant women and/or fetuses (as described in 45 CFR 46 Subpart B) be enrolled in the research?

No

E4. Neonates

Will neonates of uncertain viability or nonviable neonates (as described in 45 CFR 46 Subpart B) be enrolled in the research?

No

E5. Children

Will children be enrolled in the research?

Yes

Section F: Design/Procedure

F1. Design

Select one category that most adequately describes your research:

e) Specimen/laboratory experiment

Discuss the research design including but not limited to such issues as: probability of group assignment, potential for subject to be randomized to placebo group, use of control subjects, etc.

We propose to recruit 40 newborns every year from various NICUs in Texas for WGS, RNAseq, and metabolomics. The primary outcome will be effectiveness of Consultagene, defined as difference in diagnostic yield compared to usual care. Secondary outcomes will include 1) change in clinical care attributable to genomic results measured by adapting the harmonized measure from the Clinical Sequencing Evidence-Generating Research (CSER) consortium; and 2) caregivers' experience with and perceptions of genomic sequencing and Consultagene assessed with validated measures of caregiver outcomes. Data will be collected via Consultagene, surveys, and qualitative interviews.

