A stepped wedge cluster-randomized trial design will be used to implement the program and to evaluate the effectiveness of Consultagene (primary outcome) in providing genomic care to newborn infants in the RGV and El Paso. The Consultagene platform will be implemented in nine under-resourced NICUs, matched into cohorts based on size (number of beds), and rural/urban status. Based on those characteristics, we will have cohort triads (three NICUs each) which will be simultaneously randomized to the time at which the intervention is implemented.

Inclusion Criteria:

Inclusion criteria: Undiagnosed infants from 0-90 days of age, with a diverse group of phenotypes and strongly suspected to have genetic disorders will be recruited. Samples from biological parents will be obtained whenever available.

Clinicians will be included for interviews who use the Consultagene portal for the MAGNET study.

Exclusion Criteria:

Exclusion criteria include: (1) abnormal noninvasive prenatal testing (NIPT) suggesting chromosomal abnormality; (2) abnormal amniocentesis results, (3) abnormal newborn screening indicating an inborn error of metabolism; (4) abnormal FISH results for aneuploidy (trisomy 18, 13, or monosomy X); (5) Down syndrome; (6) dysmorphic features in the absence of other congenital anomalies; (7) isolated birth defects such as myelomeningocele, cleft lip/palate, cardiac septal defects, isolated congenital diaphragmatic hernia, etc.; (8) birth defects due to known teratogens i.e., alcohol, Isotretinoin, etc.; (9) multiple congenital anomalies associated with maternal diabetes; (10) VACTERL association; and (11) hemodynamically unstable newborns needing transport for higher level of care.

F2. Procedure

We will execute broad reliance agreements and contracts with the NICUs participating in the study after IRB approval. Baylor IRB will serve as the IRB of record for all participating sites. SMART IRB agreement will be used as the basis for reliance. An amendment will be submitted to add each participating site after the reliance agreements are established and before work commences at each site. BCM staff will conduct the research on sites.

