Based on the established inclusion and exclusion criteria, when a neonate seen by our NICU partners at level III/IV units is ascertained to need genetics consultation, the provider (neonatologist or nurse practitioner) will inform the BCM research coordinator and establish care for that patient through Consultagene portal as a peer-to-peer consultation journey. This study is based on peer to peer referral which means that patients will not be able to sign up themselves in the study. Providers will enter individuals' data into Consultagene after informed consent is obtained. Consent will be obtained by BCM research personnel and, where included in individual hospital contracts, by research coordinators at participating institutions. The research team will only obtain consent after reliance agreements have been established with different institutions.

Families accepted in the study will be contacted by the study team at BCM for video education on research study, virtual evaluation of the neonate and multi-omic study, including WGS, RNAseq, and metabolomics study. Board-certified medical geneticists and counselors at BCM will perform remote genetic evaluations using iPads at the bedside, with assistance from the local provider/research coordinator. Additional evaluations will cover various systems, and photographs will be taken with parental permission.

Research photographs taken for clinical assessment will be securely managed to protect participant privacy and confidentiality. The images will be stored on encrypted devices or secure servers, accessible only to authorized research personnel. The purpose of these photographs is to document physical features relevant to the study, enabling researchers to make accurate clinical assessments during virtual evaluations. Any identifiable information will be removed or obscured when sharing images in reports or presentations, ensuring that the photographs are used strictly for research and clinical evaluation purposes. Families will opt in for specific use of photos as per the informed consent form. The photos will not be destroyed unless the subject withdraws from the study.

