Medical records from EMR systems or documentation provided by the referring physicians will be reviewed. Medical records include prenatal, birth, and family history, radiologic and other imaging studies, echocardiogram, laboratory studies, and subspecialty consult reports for the neonates, etc for appropriate phenotyping. Blood or buccal samples from the infant and buccal samples from both parents will be collected for rapid trio GS and sent to Baylor Genetics in Houston via fedex. The WGS results will be available within 5-7 days. The first-tier evaluation focuses on detecting genetic variants, and the results will be returned through a detailed clinical report. If the first-tier testing does not provide a diagnosis, second-tier investigations, including RNA sequencing and metabolomics, may be pursued. RNA sequencing can be done on blood or skin biopsy dependent on gene expression of relevant gene(s). Skin biopsy would be completely optional.

Return of Results (ROR): Once rapid WGS results are available, a clinical report will be sent to the referring physicians, and a follow-up virtual visit will be arranged for result disclosure via Consultagene with the provider/research coordinator and family. BCM staff will communicate results and offer comprehensive genetic counseling, along with providing family support resources and disease-specific information in the family's preferred language. Recommendations for additional diagnostic studies, current therapies, clinical trials, and referrals to subspecialists or tertiary care centers for life-saving interventions will be provided to the physicians. Families will also be directed to rare disease registries and natural history studies if available for participation. Inheritance patterns, recurrence risks, and reproductive options will be discussed. Inconclusive or non-diagnostic results will also be shared with the families through the same process. A detailed report of the genomic findings and recommendations will be sent to the physicians and families, and incorporated into medical records.

The impact on patients, families, and clinicians will be evaluated through surveys and interviews.

Caregiver surveys: We will administer baseline (at enrollment) and ROR (~2 weeks after results are disclosed) surveys to the primary caregiver of all referred newborns. All surveys will be available in English and Spanish. They will be

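### The primary comparison needs diagnostic yield under usual care, but the written enrolment and data-collection procedures reach only infants referred through Consultagene

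*Protocol*

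**What the plan says.** **What the analysis requires.** Section F1 defines the primary outcome as the difference in diagnostic yield from usual care, in a stepped wedge where nine NICUs are randomised to the time of implementation. Section G1 powers the study on 4, 5 or 6 babies per NICU in each time step. Section G2 reports each NICU at each time point and fits a mixed-effects model before and after the intervention. Its denominator is all babies suspected of having a genetic diagnosis.

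**What the procedures provide.**
- Data sources (F1): "Data will be collected via Consultagene, surveys, and qualitative interviews". Section D states the matching objective as: "Determine the effectiveness of Consultagene in under-resourced NICUs via surveys and clinician interviews".
- Entry (F2): "This study is based on peer to peer referral", and providers enter "data into Consultagene after informed consent is obtained". Section J2 describes the same route.
- Record review (F2): "Medical records from EMR systems or documentation provided by the referring physicians will be reviewed". This sits within the account of how a referred infant is phenotyped.
- Caregiver surveys (F2) go at baseline and after results: "surveys to the primary caregiver of all referred newborns".
- Consent (J1): no waiver of consent and authorization is requested.
- Eligibility (F1) begins: "Undiagnosed infants from 0-90 days of age".

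**What the numbers say.** F1: "We propose to recruit 40 newborns every year from various NICUs in Texas for WGS, RNAseq, and metabolomics". G2 puts the same 40 per year, over five years, beside the before/after analysis. G1 surveys one caregiver per newborn, n=200.

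**The concern.** In a NICU that has not yet crossed over, Consultagene is not in use, so the only described entry route does not exist there. No section says how a suspected infant in such a NICU is identified, consented or followed to a diagnosis. The 10% usual-care rate in G1 is a planning estimate, not a measurement.

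Two things are at stake. If the procedures are followed literally, the primary model has no comparator, and the randomised start times contribute nothing to the primary answer. If sites find usual-care infants by another route, for example a chart search before crossover against consented referral after it, the two groups differ in how they were selected as well as in what they received. Prospective usual-care data also cannot be collected at a NICU once it has crossed over.

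**Working it through.** **1. Reproducing the stated power.** Inputs from F1 and G1: I = 9 NICUs, rates 10% and 30%, m = 4 to 6 per NICU-period, correlation (ICC) 0.5 to 0.7. Assumed, because not stated: T = 4 periods with a baseline, three NICUs crossing at each step, two-sided alpha 0.05, total variance 0.1 × 0.9 = 0.09. Hussey-Hughes variance:

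Var = I·s²(s² + T·τ²) / [(I·U − W)·s² + (U² + I·T·U − T·W − I·V)·τ²]

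Here τ² = ICC × 0.09 and s² = (1 − ICC) × 0.09 / m. U is the number of intervention cells, W the sum of squared period totals of those cells, and V the sum of squared NICU totals. U = 18, W = 126, V = 42.

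At m = 4 and ICC 0.5, τ² = 0.045 and s² = 0.01125.
- Numerator: 9 × 0.01125 × (0.01125 + 0.18) = 0.01936.
- Denominator: 36 × 0.01125 + 90 × 0.045 = 4.455.
- Variance 0.004347, SE 0.0659; power = Φ(0.20/0.0659 − 1.96) = **0.8585**, the stated lower bound.

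At m = 6 and ICC 0.7 the result is 0.9973. The stated upper figure, 99.98 (read as 0.9998), is not reproduced.

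**2. Does the match fix the number of usual-care infants?** It does not. Four layouts with three NICUs per step:

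| Layout | Usual-care cells | Infants at m = 4/5/6 | Power, lowest and highest cell |
|---|---|---|---|
| 4 periods, no baseline | 9 of 36 | 36/45/54 | 0.8585, 0.9973 |
| 4 periods, one baseline | 18 of 36 | 72/90/108 | 0.8585, 0.9973 |
| 5 periods, extra one after full rollout | 18 of 45 | 72/90/108 | 0.8901, 0.9988 |
| 5 periods, two baselines | 27 of 45 | 108/135/162 | 0.8901, 0.9988 |

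Both four-period layouts return 0.8585. The range is 9 × 4 = 36 to 27 × 6 = 162 infants.

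**3. Estimability without usual-care cells.** Keep only post-crossover cells and take period effects plus an intervention term. Four periods with a baseline leave 18 rows and 4 non-zero columns, rank 3. Five periods with the extra one after rollout leave 27 rows and 5 columns, rank 4. With all cells the ranks are full, 5 of 5 and 6 of 6. The reason is general: every remaining row has the intervention indicator equal to 1, so that column is the sum of the period columns.

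**4. Do the 200 infants include usual care?** 40 × 5 = 200. At m = 4 to 6, 36 cells hold 144 to 216 infants and 45 cells hold 180 to 270, so 200 could span both conditions. Split in proportion to cells, usual care would then be 200 × 9/36 = 50, 200 × 18/36 = 100, 200 × 18/45 = 80 or 200 × 27/45 = 120. G1 says none of the nine sites has performed WGS at baseline, so these infants would not fit F1's statement that the 40 per year are recruited for WGS. F2 makes RNAseq and metabolomics second-tier, so the conflict concerns WGS.

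**The case against.** The strongest reply is that the protocol commits to control data: G1 speaks of data in each time step and G2 of before and after at each NICU. That stands. A reader might infer from the procedures that no control data are planned, and G1 and G2 contradict that inference. They state the need, however, without a source, a consent route or a count.

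A second reply is that F1's data-source sentence is a one-line summary and that F2 allows review of electronic records. The sentence alone would be weak evidence. But F2 describes that review for infants who have a referring physician, within the Consultagene pathway. Consenting usual-care infants would be compatible with the J1 answer, but no such step is described.

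A third reply is that the 200 may span both conditions, which leaves only loose wording about WGS. That reading is coherent, and G2 does not say outright that the 200 are its denominator. The text therefore leaves the matter unclear; it does not show that all 200 are intervention infants.

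Finally, this could be left to the SAP. A SAP can set the model, but it cannot authorise chart access or recover infants who were never ascertained.

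**Conclusion.** The concern holds as a conflict between the stated analysis and the stated enrolment and data-collection procedures, and it affects the primary outcome. Followed as written, the procedures yield no usual-care cells and the effect is not estimable. This does not depend on the number of periods. The risk of confounding is conditional: it arises only if usual-care infants are found by a different route from referred infants.

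A reader might take the match to 0.8585 as proof that 72 to 108 usual-care infants are needed. It is not, because a layout without a baseline gives the same power with half as many usual-care cells. Given three NICUs per step and four or five periods, the range is about 36 to 162, and no single count should be asserted. The non-estimability result describes what literal execution would produce, not what the sponsor intends.

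**What to change.** - **F1/F2:** ascertain infants by the same screening log or chart abstraction in every NICU-period, before and after crossover, whether or not they are referred or sequenced, with the same follow-up window.
- **Population:** state one primary-analysis population for both conditions. Reconcile F1 eligibility, including its exclusions, with G1's babies needing genetic screening and G2's babies suspected of a genetic diagnosis; these differ. For the analysis, judge undiagnosed status at first genetic suspicion, so that a usual-care diagnosis by karyotype or microarray counts as an outcome and not as an exclusion.
- **J1:** request a waiver for this record review, or describe a consent route for usual-care infants.
- **G1:** state the number of periods, whether there is a baseline period, and the usual-care and intervention counts, reconciled with 40 per year and n=200.
- **Section D and F1:** align the data-source sentences with the above.

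The cost is an IRB amendment, possible updates to site agreements, and chart abstraction at nine NICUs, including eligible infants who are not referred after crossover. The protocol gives no basis for costing that effort. No additional sequencing is needed. The change should be in place before the first NICU crosses over.
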